6.2. Subject Exclusion Criteria

The presence of any of the following will exclude a subject from study enrollment:

1. Known fibrolamellar HCC or mixed hepatocellular-cholangiocarcinoma.
2. Subjects with untreated or incompletely treated varices with bleeding or high risk for bleeding are excluded with the following clarification: subjects with history of prior variceal bleeding must have been treated with adequate endoscopic therapy without any evidence of recurrent bleeding for at least 6 months prior to study entry and must be stable on optimal medical management (e.g. non-selective beta blocker, proton pump inhibitor) at study entry.

3. Subjects with QTcF interval \geq 480 milliseconds or with risk factors for torsade de pointes (e.g., heart failure, uncontrolled hypokalemia, family history of long QT syndrome) or receiving treatment with concomitant medications known to prolong the QT/QTc interval that cannot be replaced with another treatment.
4. Ascites defined as CTCAE Grade \geq 2. Subjects who have been on a stable medication regimen for at least 2 months to manage ascites are eligible if they show ascites Grade < 2. Subjects with clinically undetectable ascites who are Child A with detectable ascites at CT/MRI are eligible.
5. Uncontrolled high blood pressure (systolic blood pressure, SBP $>$ 150 mmHg and/or diastolic blood pressure, DBP $>$ 95 mmHg, despite optimal treatment, on at least 2 out of 3 determinations repeated at 30 minutes interval and done in case that the first one meets the criterion for exclusion).
6. Direct-Acting Antivirals (DAA) at the time of treatment start; previous HCV treatment with DAAs is allowed.
7. Clinical evidence of hepatic encephalopathy.
8. Known brain metastases or evidence of leptomeningeal disease.
9. Known history of allergic reactions to polysorbate 80.
10. Any of the following in the past 6 months: myocardial infarction, uncontrolled cardiac arrhythmia, unstable angina, coronary/peripheral artery bypass graft, symptomatic congestive heart failure, cerebrovascular accident or transient ischemic attack, pulmonary embolism, deep vein thrombosis (except chronic/stable portal vein thrombosis).
11. Major surgery, other than diagnostic surgery, within 4 weeks before treatment start.
12. Any anticancer agent within 4 weeks or, in absence of toxicity, 5 half-lives (within 6 weeks for nitrosureas, mitomycin C and liposomal doxorubicin) before treatment start.

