9.2.3. Dose Modifications

9.2.3.1. Dose Reductions/Treatment discontinuations

Dose reductions/treatment discontinuations may occur as a consequence of drug-related toxicities, during a cycle or at the start of a new cycle. All dose reductions/treatment discontinuations should be based on the most severe toxicity observed in the previous cycle and attributable to the study drug (according to the NCI CTCAE v 5.0). In the event of multiple toxicities, the dose reduction/treatment discontinuation should be based on the worst toxicity observed.

Any modification to the NMS-01940153E dose should be documented in the eCRF.

During treatment, doses can be de-escalated only twice, otherwise patients would have to be withdrawn.

Doses reduced for drug-related toxicity should generally not be re-escalated, even if there is minimal or no toxicity with the reduced dose according to [Table 6](#). However, intra-patient re-escalation back to the previous dose level may be permitted at the discretion of the Investigator after discussion with the Sponsor.

Recommended dose reductions or discontinuation criteria during the treatment cycle and at the start of the subsequent cycle are shown in [Table 6](#).

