9.2.3.2. Re-treatment Criteria and Cycle Delay

A new cycle of treatment may begin when hematological and non-hematological toxicities are Grade ≤ 1 or have recovered to baseline values.

If these conditions are not met, treatment should be delayed for 1 week to allow for recovery. If, after 1-week delay, re-treatment criteria are met, then the new cycle can be initiated with a starting dose defined based on the toxicities observed in the previous cycle as outlined in the [Table 6](#).

If, after this period, toxicities do not recover to the pre-defined level, the patient will be withdrawn from the treatment, unless the Investigator believes treatment continuation is in the patient best interest. In this case, a maximum delay of 2 weeks (up to day 42 from cycle start) will be allowed.

Table 6. Dose Reductions/Treatment Discontinuations for NMS-01940153E Based on the Worst Grade (as per NCI CTCAE Criteria, Version 5.0) Observed During a Treatment Cycle and in the Prior Treatment Cycle

Toxicity	Dose Adjustment during treatment cycle	Next cycle Starting Dose
Hematological Toxicities		
Neutropenia Grade 3	Omit dose; when resolved to \leq Grade 1 within the same cycle, decrease one dose level.	Start at or maintain the decreased dose level.
Neutropenia Grade 4	Omit dose; when resolved to \leq Grade 1 within the same cycle, decrease one dose level.	Start at or maintain the decreased dose level.
Febrile Neutropenia	Omit dose; when resolved, decrease one dose level.	Start at or maintain the decreased dose level.
Thrombocytopenia Grade 3 associated with bleeding or thrombocytopenia Grade 4	Omit dose; when resolved to \leq Grade 2 within the same cycle, decrease one dose level.	Start at or maintain the decreased dose level.
Anemia Grade 3	Omit dose; when resolved to \leq Grade 2 within the same cycle, decrease one dose level.	Start at or maintain the decreased dose level.
Anemia Grade 4	Study treatment discontinuation.	Study treatment discontinuation.
Other Grade 3 Hematologic Toxicities	Omit dose; when resolved to \leq Grade 2 within the same cycle, decrease one dose level.	Start at or maintain the decreased dose level.
Other Grade 4 Hematologic Toxicities	Study treatment discontinuation.	Study treatment discontinuation.
Nausea and/or Vomiting		
Grade \geq 3 despite optimal management of the event §‡	Omit dose; when resolved to \leq Grade 2 within the same cycle, decrease one dose level.	Start at or maintain the decreased dose level.
Diarrhea		

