Grade 2 despite optimal management of the event §	Omit dose; within the same cycle decrease one dose level.	Start at or maintain the decreased dose level.
Grade \geq 3 despite optimal management of the event §	Omit dose; when resolved to \leq Grade 2 within the same cycle, decrease one dose level.	Start at or maintain the decreased dose level.
Neurologic Toxicities (except insomnia/paraesthesia)		
Grade 2	Omit dose; when resolved to \leq Grade 1, decrease one dose level.	Start at or maintain the decreased dose level.
Grade $>$ 2	Consider discontinuation of study treatment based on risk/benefit assessment #.	Consider discontinuation of study treatment based on risk/benefit assessment #.
Other Non-Hematological Toxicities (except alopecia)		
Intolerable or persistent Grade 2 adverse events	Omit dose; when resolved to \leq Grade 2, maintain the dose level at first occurrence; at second occurrence, omit dose; when resolved to \leq Grade 2, decrease one dose level. .	At second occurrence, start at or maintain the decreased dose level.

Table 6. Dose Reductions/Treatment Discontinuations for NMS-01940153E Based on the Worst Grade (as per NCI CTCAE Criteria, Version 5.0) Observed During a Treatment Cycle and in the Prior Treatment Cycle

Toxicity	Dose Adjustment during treatment cycle	Next cycle Starting Dose
Grade 3	Omit dose; when resolved to \leq Grade 2, decrease one dose level.	Start at or maintain the decreased dose level.
Grade 4	Omit dose; when resolved to \leq Grade 2, decrease one dose level or consider study treatment discontinuation [#]	Start at or maintain the decreased dose level or consider study treatment discontinuation [#]
Grade \geq 3 hypersensitivity reaction suggestive of anaphylactic reaction [#]	Study treatment discontinuation	Study treatment discontinuation.

§ For prophylaxis and management of the events, see details in Supportive Care Sections 9.2.7.
 ‡ lasting longer than 48h without resolution to grade 2 or better and judged at least possibly related to NMS-01940153E.

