 # Investigator to discuss risk/benefit with Sponsor, if positive, decrease one dose level.

9.2.4. Extension Treatment

Not applicable.

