10. SUBJECT WITHDRAWAL FROM STUDY PARTICIPATION

Patients may withdraw from the study at any time at their own request, or they may be withdrawn at any time at the discretion of the Investigator or Sponsor for safety, behavioral, or administrative reasons.

If the patient does not return for a scheduled visit, every effort should be made to contact him/her. In any circumstance, every effort should be made to document patient outcome, if possible. The Investigator should inquire about the reason for withdrawal, request the patient to return for a final visit, if applicable, and follow-up with the patient regarding any unresolved adverse events.

If the patient withdraws consent for disclosure of future information, no further evaluations should be performed and no additional data should be collected. The Sponsor may retain and continue to use any data collected before such withdrawal of consent.

Patients may continue with therapy unless any of the following occurs:

- Disease progression by RECIST 1.1 at any time, unless there is reasonable evidence of clinical benefit to justify continuation on treatment, to be discussed with the Sponsor;
- Unacceptable drug-related toxicities incompatible with continuation of treatment with NMS-01940153E according to the judgment of the Investigator, even at a reduced dose;
- Any medical event requiring administration of an unauthorised concomitant treatment if it interferes with the study evaluations and/or if it jeopardises patient's safety (see Section 9.2.7);
- Change in the patient's medical status (including pregnancy) such that the Investigator believes that patient safety may be compromised or that it would be in the best patient's interest to stop treatment;
- Occurrence of permanent or significant incapacity or disability;
- Treatment delay for >1 week from day 28 of any cycle due to treatment related toxicity, unless the investigator believes treatment continuation is in the best patient's interest. In this case a maximum delay of 2 weeks is allowed;
- More than two dose de-escalations required;
- Substantial deviation from specified inclusion or exclusion criteria or non-compliance by the patient with protocol requirements;
- Patient's refusal to continue study treatment;
- Withdrawal of consent;

- Patient lost to follow up;
- Death;
- Study terminated by the Sponsor.

Patients will be withdrawn from the study in case of:

- Withdrawal of consent;
- Patient lost to follow up;
- Death;

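### Table 6 orders a stop after a Grade ≥3 anaphylactic-type reaction, but footnote # on the row label permits a lower dose after a positive Investigator-Sponsor risk/benefit discussion

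*Protocol*

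**What the plan says.** Table 6 in Protocol Section 9.2.3.2 gives, for each toxicity, an action during the cycle and a starting dose for the next cycle. The last row covers a Grade ≥3 "hypersensitivity reaction suggestive of anaphylactic reaction". Both of its action cells say that study treatment is discontinued. Neither cell offers a reduced dose or asks the site to weigh anything.

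The label of that row carries the mark #. The footnote under the table reads: "Investigator to discuss risk/benefit with Sponsor, if positive, decrease one dose level".

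The same mark appears in two other rows, each time inside the action cells. For neurologic toxicity above Grade 2 the cells read "Consider discontinuation of study treatment based on risk/benefit assessment". For other non-hematological Grade 4 toxicity the within-cycle cell includes "decrease one dose level or consider study treatment discontinuation", and the next-cycle cell gives the same choice.

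Two further rows order discontinuation in both columns: "Anemia Grade 4" and other Grade 4 hematologic toxicities. Neither carries #.

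**The concern.** One row gives two instructions for the same event. The cells end treatment. The footnote on the label lets treatment continue at a lower dose if the discussion favours it. A physician managing a suspected anaphylactic reaction needs to know whether stopping is an absolute rule or a default with an exception, and the table does not say.

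What is at stake is patient safety. Read with the footnote, the protocol contains a written route to giving the drug again after a potentially life-threatening reaction. Elsewhere the protocol is cautious about allergy: exclusion criterion 9 in Section 6.2 bars patients with "Known history of allergic reactions to polysorbate 80". An on-study reaction attributed to that excipient would give a patient the very history that criterion excludes, yet # would still leave room for another dose.

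**Working it through.** The plan gives no figure to reproduce. The check is a count of marks and a comparison of texts.

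**1. Every # in Table 6**

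| Row | Where # sits | What the action cells say |
|---|---|---|
| Neurologic, Grade >2 | both action cells (2) | consider stopping |
| Other non-hematological, Grade 4 | both action cells (2) | reduce, or consider stopping |
| Grade ≥3 anaphylactic-type hypersensitivity | row label (1) | stop |

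Total: 2 + 2 + 1 = 5. Four marks are attached to a decision left open, which the footnote explains how to take. The fifth is attached to a row in which the cells leave no decision open.

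**2. Rows that order a stop in both columns**

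These are anemia Grade 4, other Grade 4 hematologic toxicities, and the anaphylactic-type reaction: 3 rows. Of these, 1 carries #.

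**3. The row read both ways**

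- Cells alone: treatment ends.
- Cells plus #: treatment ends by default, and may resume one level lower if the Investigator's discussion with the Sponsor is positive.

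The second reading can be compared with the general non-hematological rows. The Grade 3 row omits the dose and reduces one level once the event is Grade 2 or lower, with no Sponsor discussion. The Grade 4 row also carries #, but it lists reduction first and stopping only as something to consider. The anaphylactic-type row with # therefore remains the strictest of the three, because its default is to stop for both grades and any exception passes through the Sponsor. What changes is that re-exposure, which the cells rule out, becomes possible.

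**4. Text elsewhere that might settle it**

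- Section 9.2.3.1 introduces the table as "Recommended dose reductions or discontinuation criteria during the treatment cycle" and the following cycle. It sets no precedence between a cell and a footnote.
- Section 10 lists among the reasons for stopping: "Unacceptable drug-related toxicities incompatible with continuation of treatment with NMS-01940153E according to the judgment of the Investigator, even at a reduced dose". It leaves the matter to judgment and does not mention anaphylaxis.
- Section 9.2.7.4 allows antihistamine or corticosteroid prophylaxis if signs of polysorbate 80 intolerance emerge. It names no grade and says nothing about re-treatment after a Grade ≥3 anaphylactic-type reaction.
- The SAP does not address the rule.

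None of these says which instruction governs.

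**The case against.** The strongest reply is that a footnote may qualify a row without contradicting it. A default stop, with an exception only after a Sponsor discussion, is a coherent policy and may be what was meant. This stands in part. The documents do not show intent, so the mark can only be called probably misplaced. But if an exception was intended, both cells are worded too absolutely, and the table needs correction either way.

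Other safeguards also limit the consequence. Section 10 lets the Investigator stop when patient safety may be compromised. Serious events reach Sponsor Pharmacovigilance within 24 hours (Section 11.5.1.7). Two or more patients with Grade 4 events put the study on hold (Section 12.4), and the DSMB reviews safety periodically (Section 12.5). All of this stands, but none of it tells the site which instruction in the row to follow.

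Two stronger readings are tempting and should be set aside.

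- A reader might infer that # leaves the row without a purpose, because the general rows already allow a reduction. They do, but without a default stop, and for Grade 3 without a Sponsor discussion. The row keeps a function.
- A reader might infer that sites would manage the same event in widely different ways. The same Sponsor takes part in every discussion under #, so divergence between sites is limited, and no site is told to re-treat on its own authority.

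Finally, the table was read from PDF by a program and the page layout could not be seen. The mark has the same form here as in the Grade 4 row directly above it, so a reading artefact is unlikely but not excluded.

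**Conclusion.** The inconsistency is real and worth fixing. The cells order discontinuation, while the footnote on the label permits a conditional return one dose level lower. The pattern of the other marks (four of five on cells that say to consider stopping, and none on the other two mandatory-stop rows) makes misplacement the likelier explanation.

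The size of the point is one mark in an operative dosing rule, with a possible re-exposure after suspected anaphylaxis as its consequence. It would be wrong to infer that the protocol allows unconditional re-treatment: a positive Investigator-Sponsor discussion is required. Nor do the documents support any statement about how often such reactions occur, and none is made. No effect on response rate, analysis or sample size is claimed.

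The conclusion assumes that the mark stands on the label in the original page as it does in the text, and that no unseen document, such as the Study Manual, already settles the matter.

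**What to change.** In Table 6, delete # from the label of the Grade ≥3 anaphylactic-type hypersensitivity row, so that discontinuation is unconditional. Leave both action cells of that row unchanged, and keep # on the neurologic Grade >2 and other non-hematological Grade 4 rows, where it fits.

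The cost is one mark in the next amendment and a notice to sites. Assessments, sample size and analysis are unaffected. The small downside is the loss of a Sponsor-gated exception, which the row's own cells do not offer.

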 # Investigator to discuss risk/benefit with Sponsor, if positive, decrease one dose level.

9.2.4. Extension Treatment

Not applicable.

9.2.5. Overdose Instructions

There are no known antidotes for NMS-01940153E overdose. All cases of overdose [associated or not to an adverse event/serious adverse event (AE/SAE)] and medication errors accompanied by an AE/SAE, should be notified, using the SAE form, to the Sponsor Pharmacovigilance immediately (i.e. within 24 hours) according to procedures described in part 11.5.1.7. Study monitor should be also contacted to discuss the details of any overdose.

Whether or not the overdose/medication error is accompanied by an AE, as determined by the Investigator, the overdose/medication error and, if applicable, any associated AE must be captured on the AE eCRF page (refer to Safety Assessments, Section 11.5, for further details).

9.2.6. Unblinding

Not applicable.

9.2.7. Concomitant Medications and Other Therapy

Any medication the patient takes other than the study treatment, including herbal and other non-traditional remedies, is considered a concomitant medication. All information concerning concomitant medication taken (started or completed) up to 28 days before the start of treatment with NMS-01940153E and within 28 days (and, if applicable, no more than 35 days) from last study drug administration, should be collected on the electronic case report form (eCRF): name, active ingredient, reason for use, route of administration, strength and unit, frequency or total daily dose, start and stop dates. Any change in the dosage or regimen of a concomitant medication must be recorded in the eCRF.

Prior treatments for the disease under study are to be collected on separate and appropriate forms of the eCRF and should cover the entire tumour history.

Directives for supportive care of the patients are outlined below and could be adapted according to institutional practices; however they cannot ever include strong inducers of flavin-containing monooxygenase 1 (FMO1), FMO3 as well as sensitive cytochrome 3A4 (CYP3A4) substrates, CYP3A4 and BCRP (breast cancer resistance protein) substrates with narrow therapeutic index (NTI). See [Appendix 3](#) and [Appendix 4](#) for details.

9.2.7.1. Antiemetics Support

Mild nausea and vomiting have been reported in the FIH study (EudraCT 2014-002023-10). Among 38 patients who received NMS-01940153E, nausea was reported in 12 patients (31.6%), with only one patient experiencing grade 3. Grade 1-2 vomiting was reported in 9 patients (23.7%).

Prophylactic therapy with antiemetics, administered according to hospital guidelines, is allowed including during cycle 1, if deemed appropriate.

Antiemetic therapy can be administered at Investigator's discretion whenever needed, including during cycle 1.

9.2.7.2. Antidiarrheal Support

The use of antidiarrheal agents is allowed according to hospital guidelines along with antibiotic treatment and IV hydration, if indicated. Patients should be instructed to refer to the centre in case of: diarrhoea lasting > 24 hours despite optimal supportive care or diarrhea with fever; black or bloody stools; symptoms of dehydration such as lightheadedness, dizziness, or faintness and inability to take liquids by mouth due to nausea and vomiting.

9.2.7.3. Hematopoietic Support

Red blood cell and/or platelets transfusion: during treatment should be considered at the Investigator's discretion in patients with significant anaemia and/or thrombocytopenia; transfusions are however not allowed within 72h before treatment start. Folates may be indicated also for anaemia treatment.

Hematopoietic growth factors

In the dose escalation part, prophylactic use of G-CSF or initiation of erythropoietin in Cycle 1 is not permitted but may be instituted in Cycle ≥ 2 in patients who are having difficulty with severe neutropenia or anemia. Patients who have been treated for ≥ 4 weeks with erythropoietin prior to the first cycle may continue the existing treatment.

Growth factors may be used as medically indicated in patients with relevant neutropenic complications, such as tissue infection, sepsis, etc., or anemia, at the Investigator's discretion. Patients with neutropenic fever or infection should be hospitalized promptly for IV antibiotic

therapy and may receive therapeutic CSFs as appropriate. Treatment of relevant neutropenic complications (e.g. tissue infection, sepsis, etc.) is left at the Investigator's discretion and should be done according to the hospital guidelines for treating these types of events.

9.2.7.4. Prophylaxis for Polysorbate 80 intolerance

Intolerance: prophylactic treatment is not allowed before Cycle 1. In case the toxicity profile emerging during the study suggests that there might be signs of intolerance to polysorbate 80, prophylaxis with antihistaminic or corticosteroids according to centre practices could be implemented.

9.2.7.5. Other Permitted Concomitant Medications

Therapies considered necessary for the patient's wellbeing may be given at the discretion of the Investigator, i.e. chronic treatments for concomitant medical conditions, as well as agents required for life-threatening medical problems, analgesics etc. according to the drug-drug interaction information. In particular, strong inhibitors of FMO1 and FMO3, moderate substrates of CYP3A4 and CYP3A4/BCRP substrates with no NTI should be used with caution (see [Appendix 4](#)).

Precaution should be used in treatment of NMS-01940153E with concomitant drugs that are known to prolong QT or QTc intervals, since the potential effect of study drug on QT prolongation has not been fully evaluated in humans. The Investigator should consult individual labels for concomitant medication. If medically indicated, a cardiology consult should be obtained.

Whenever possible the administration of drugs that may cause drug-drug interaction should not be done concomitantly with NMS-01940153E.

Patients should be advised to contact the treating physician before starting any new drug.

